### 3. Study Variables and Database

#### 3.1. Main variable:

Area under the serum progesterone curve during ovarian stimulation

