## Protocol Synopsis

---

Protocol Title: Follicular Esteroidogenesis in Controlled Ovarian Stimulation

---

EudraCT Code: 2015-005762-28

---

Sponsor's protocol version and date: 1.0 of 12/1/2015

---

Sponsor:

IVI Valencia

[name]

[contact]

[[name] / [name]]

---

Principal Investigator:

[name]

Instituto Valenciano de Infertilidad

[contact]

[name]/[name]

---

Phase: Fase IV

---

Centros participantes:

IVI Valencia

---

Investigational Medicinal Product (IMP): Recombinant FSH, Highly Purified HMG, Ganirelix, Triptorelin

---

Primary Objective: To compare the serum concentrations of the different hormones involved in follicular steroidogenesis during an EOC cycle between FSHr and hpHMG.

---

Secundary Objectives:

- Define the area under the curve for each of the follicular steroids along the EOC in cycles stimulated with FSHr and hpHMG.
- Calculate the contribution to the circulation of each of the follicular steroids per unit of follicular volume.
- To identify the metabolic pathways of follicular steroidogenesis as a function of the type of gonadotrophin used for COC.
- To compare the concentration of steroids in follicular liquid in stimulated cycles with FSHr and hpHMG.
- Correlate the hormone levels observed in serum with the concentration in follicular fluid]

---

Methodology: 110 women will be included (55 in each study group, i) FSHr; ii) hpHMG) with normal ovarian function, who will follow ovarian stimulation in cycle with GnRH Antagonists. For greater uniformity in the study population, oocyte donors will be used.

Serum extractions and transvaginal ultrasound for folliculometry will be performed on the days of stimulation 1, 4, 6, 8 and the day of administration of the triptorelin. In the follicular puncture for the extraction of the oocytes, the first follicle will be individually aspirated to obtain the follicular fluid. The samples obtained will be frozen and stored at -80°C for later analysis.

In each serum sample they will be determined: Pregnenolone, Progesterone, 17-OH-Progesterone, Dehydroepiandrosterone, Androstenodione, Testosterone, Estrone and Estradiol.

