**Number of subjects: 110**

A previous study conducted by our group (Bosch et al, 2008) in which these two same protocols were compared in terms of clinical outcomes, showed that the serum P on the last day of stimulation was  $0.73 \pm 0.42$  in the HMG group vs  $0.99 \pm 0.48$  in the FSH group ( $p<0.001$ ). According to these data, to determine a difference of this magnitude with a 95% confidence level (5% alpha error) and 80% power (20% beta error), 48 patients per group are required. Assuming a loss rate of 15%, 55 patients should be randomly assigned to each group, i.e. 110 patients in total

---

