### 2. Sample size

A previous study conducted by our group (Bosch et al, 2008) in which these two same protocols were compared in terms of clinical outcomes, showed that the serum P on the last day of stimulation was  $0.73 \pm 0.42$  in the HMG group vs  $0.99 \pm 0.48$  in the FSH group ( $p<0.001$ ). According to these data, to determine a difference of this magnitude with a 95% confidence level (5% alpha error) and 80% power (20% beta error), 48 patients per group are required. Assuming a loss rate of 15%, 55 patients should be randomly assigned to each group, i.e. 110 patients in total.

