#### 3.2. Secondary variables:

- Area under the serum estradiol curve during ovarian stimulation
- Area under the serum Pregnenolone curve during ovarian stimulation
- Area under the 17-OH serum progesterone curve during ovarian stimulation
- Area under the serum Androstenodione curve during ovarian stimulation
- Area under the serum Dehydroandrostenedione curve during ovarian stimulation
- Area under the serum Testosterone curve during ovarian stimulation
- Area under the curve of Serum Estrone during ovarian stimulation
- Area under the serum FSH curve during ovarian stimulation
- Area under the serum LH curve during ovarian stimulation
- Concentration of P in follicular liquid
- Concentration of Estradiol in follicular liquid
- Concentration of Pregnenolone in follicular liquid
- Concentration of 17-OH Progesterone in follicular liquid
- Concentration of Androstenodione in follicular liquid
- Concentration of Dehydroepiandrostenodione in follicular liquid
- Concentration of Testosterone in follicular liquid
- Concentration of Estrone in follicular liquid

- Concentration of FSH in follicular liquid
- Concentration of LH in follicular liquid

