### 4.3. Analysis of the working hypothesis:

Each hormonal determination of each day of stimulation in which it is determined will be compared by means of Student "t" for independent samples, once the normal distribution of the values by means of the tests of Kolmogorov-Smirnov and Shapiro-Wilks has been verified. Otherwise, comparisons will be made with the Mann-Whitney test. The area under the curve during ovarian stimulation will be calculated for each of the hormones included in the study, and both groups will be compared equally. The proportion of patients with elevated Progesterone on the last day of stimulation ( $>1.5 \text{ ng/mL}$ ) will

be compared between both groups by Chi-square test. For this particular event the relative risk and its 95% confidence interval will also be calculated.

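### The only stated power (80% at 48 per group) is for last-day serum progesterone; for the declared main variable, the progesterone AUC, no difference, SD or power is reported, and the synopsis names a different primary

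*Combined protocol and SAP*

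**What the plan says.** **Main variable.** Section 3.1 lists a single item: "Area under the serum progesterone curve during ovarian stimulation".

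**Sample size.** Section 2, repeated in the synopsis under Number of subjects, relies on an earlier study by the same group, which "showed that the serum P on the last day of stimulation was" 0.73 ± 0.42 with HMG and 0.99 ± 0.48 with FSH. At 5% alpha and 80% power it concludes that "48 patients per group are required", and it raises this to 55 per group for 15% loss.

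**Objectives.** The synopsis gives the primary objective as "To compare the serum concentrations of the different hormones involved in follicular steroidogenesis during an EOC cycle between FSHr and hpHMG". The AUCs come under the secondary objectives: "Define the area under the curve for each of the follicular steroids along the EOC in cycles stimulated with FSHr and hpHMG".

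**Analysis.** In Section 4.3, "Each hormonal determination of each day of stimulation in which it is determined will be compared" by t test, or by Mann-Whitney if normality fails. The AUCs are compared in the same way. The proportion with progesterone above 1.5 ng/mL on the last day is compared by chi-square. An interval is planned only for that proportion: "For this particular event the relative risk and its 95% confidence interval will also be calculated".

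**Secondary variables.** Section 3.2 lists the AUCs of the other hormones and the follicular-fluid concentrations (for example "Concentration of P in follicular liquid"). It does not list last-day serum progesterone.

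**The concern.** A power statement should belong to the variable that decides the trial. Here it belongs to one time point, while the declared main variable summarises the whole stimulation period. Nothing in the documents says why the last-day effect should carry over to the AUC. The reader therefore has neither a power nor a detectable difference by which to judge the study size for the main variable.

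This matters most if the AUC comparison is not significant. Its power would be unknown, and no interval is planned to show which differences remain compatible with the data.

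The synopsis makes this harder to resolve. Its primary objective covers several hormones and is worded in concentrations, whereas Section 3.1 covers one hormone and one summary measure. A reader cannot tell from the two together which result is decisive.

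**Working it through.** **Inputs.** From Section 2: means 0.73 and 0.99, SDs 0.42 and 0.48, alpha 5%, power 80%, loss 15%, 55 randomised per group. From the synopsis: 1:1 allocation, and samples on days 1, 4, 6, 8 and the triptorelin day. Sidedness is not stated; two-sided is assumed because it reproduces the plan's figure (one-sided gives 38).

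**Step 1: reproduce the plan's figure.**
- Pooled SD = √((0.42² + 0.48²)/2) = 0.451
- Standardised difference = (0.99 − 0.73)/0.451 = 0.26/0.451 = 0.576
- n per group = 2 × ((1.960 + 0.842) × 0.451/0.26)² = 47.2, rounded up to **48**, as stated

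With the noncentral t distribution, power for last-day progesterone is 79.8% at 48 per group and 85.0% at 55. The plan's own loss rate leaves 55 × 0.85 = 46.75 per group, where power is 78.1% (46) to 79.0% (47).

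**Step 2: can that power be carried to the AUC?** The AUC combines five samples. Its standardised difference depends on the group differences and SDs at the four earlier times, on the correlations between times, and on stimulation length. The documents give none of these; they give figures for the last time point only. No AUC power can be computed from them.

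**Step 3: what can be computed.** The table shows the standardised AUC difference that has 80% power (two-sided 5% t test), and the half-width of a 95% interval for the difference in means, t(0.975, 2n − 2) × √(2/n), in SD units.

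| Evaluable per group | Difference with 80% power (SD) | 95% CI half-width (SD) |
|---|---|---|
| 46 | 0.590 | 1.987 × √(2/46) = 0.414 |
| 48 | 0.578 | 1.986 × √(2/48) = 0.405 |
| 55 | 0.539 | 1.982 × √(2/55) = 0.378 |

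**Step 4: sensitivity to an assumed AUC effect.** The effects below are assumptions; none is in the documents.

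| Assumed AUC difference (SD) | Power, n = 46 | Power, n = 48 | Power, n = 55 | n per group for 80% |
|---|---|---|---|---|
| 0.3 | 29.6% | 30.7% | 34.5% | 176 |
| 0.4 | 47.5% | 49.2% | 54.7% | 100 |
| 0.5 | 66.0% | 67.9% | 73.9% | 64 |
| 0.7 | 91.3% | 92.4% | 95.3% | 34 |

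The range shows how strongly the answer depends on the missing figure. It does not show which row applies.

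**Step 5: the two statements of what is primary.**
- Synopsis: primary is the comparison of serum concentrations of several hormones; the AUCs are secondary.
- Section 3.1: primary is the AUC of progesterone alone.
- Sample size: progesterone at one time point.

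The powered quantity falls within the scope of the synopsis objective but is not singled out there, and it is not the variable in Section 3.1.

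**The case against.** The best defence is that the planning variable is close to the main one. It is the same hormone, and the trigger-day sample is the last point on the curve. The text says openly which variable was used, and the arithmetic is right. All of this stands, and it makes the problem a gap in justification, not a calculation error. It does not transfer the 80%, because the plan neither claims that the effect carries over nor gives anything to support it.

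A reader might infer that the trial is underpowered for its main variable. The documents do not support that: the AUC effect in SD units could be larger or smaller than 0.576, and the lower rows of power in the sensitivity table rest on assumed values only.

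A reader might also infer that last-day progesterone has been left out of the analysis. It has not. Section 4.3 compares it as a daily value and as the proportion above 1.5 ng/mL; it is only missing from the lists in 3.1 and 3.2.

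It can be said, too, that comparing concentrations across a cycle may be summarised by an AUC, and that the secondary objective speaks of defining the AUCs, not comparing them. On that reading the synopsis and Section 3.1 are loosely aligned, not flatly opposed. That is fair, but an objective covering several hormones still does not identify progesterone, or its AUC, as the single deciding variable.

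Finally, Section 4.1 plans means and SDs for the study variables. If these are given by group, which it does not say, a reader could work out an interval. That softens the point about intervals but does not replace a planned one.

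**Conclusion.** The concern holds in a limited form and should be fixed. The 80% power at 48 per group is correct for last-day serum progesterone and is not established for the progesterone AUC, for which no difference, SD or power is reported. The true AUC power is unknown in either direction.

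What can be stated is the condition: 80% power for the AUC needs a standardised difference of about 0.59, 0.58 or 0.54 with 46, 48 or 55 evaluable per group. This assumes a two-sided 5% t test and does not carry over unchanged to the Mann-Whitney branch in Section 4.3.

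Separately, the synopsis and Section 3.1 do not name the same primary and need reconciling. Confidence is high on the mismatch itself. Nothing here shows that the trial is too small.

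**What to change.** 1. **Name one primary variable.** Before any group comparison is seen, make the synopsis and Section 3.1 name the same single variable. The sponsor chooses between the progesterone AUC and last-day serum progesterone, on which the trial was sized. The other is listed as secondary.

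2. **Match the power statement to that choice**, in Section 2 and in the synopsis.
   - If the AUC stays primary, add: *The 80% power refers to last-day serum progesterone. No AUC planning estimate is reported; with a two-sided 5% t test, 80% power for the progesterone AUC requires a standardised difference of about 0.59 with 46 evaluable per group (55 less 15%), 0.58 with 48, or 0.54 with all 55.* If a sourced AUC difference and SD exist, give those and the resulting power instead, even if it is below 80%.
   - If last-day progesterone becomes primary, keep the existing calculation and state its power after loss: about 78% to 79% at 46 to 47 per group.

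3. **Report the AUC effect with its uncertainty.** In Section 4.3, give the between-group AUC difference with a 95% confidence interval: the difference in means with the t test, or the Hodges-Lehmann shift with its interval if Mann-Whitney is used.

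**Cost.** Wording in the synopsis and in Sections 2, 3 and 4.3, plus one estimate and interval from data already planned. The power statement becomes slightly less favourable. No extra patients are needed. If a sourced AUC effect turns out to be below about 0.54 SD, power is under 80% even with all 55 analysed; the fix is to say so, and whether to enlarge the trial is a separate decision for the sponsor.

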#### 3.2. Secondary variables:

- Area under the serum estradiol curve during ovarian stimulation
- Area under the serum Pregnenolone curve during ovarian stimulation
- Area under the 17-OH serum progesterone curve during ovarian stimulation
- Area under the serum Androstenodione curve during ovarian stimulation
- Area under the serum Dehydroandrostenedione curve during ovarian stimulation
- Area under the serum Testosterone curve during ovarian stimulation
- Area under the curve of Serum Estrone during ovarian stimulation
- Area under the serum FSH curve during ovarian stimulation
- Area under the serum LH curve during ovarian stimulation
- Concentration of P in follicular liquid
- Concentration of Estradiol in follicular liquid
- Concentration of Pregnenolone in follicular liquid
- Concentration of 17-OH Progesterone in follicular liquid
- Concentration of Androstenodione in follicular liquid
- Concentration of Dehydroepiandrostenodione in follicular liquid
- Concentration of Testosterone in follicular liquid
- Concentration of Estrone in follicular liquid

- Concentration of FSH in follicular liquid
- Concentration of LH in follicular liquid

### 3.3. Control variables

- Total number of oocytes
- Number of mature oocytes (metaphase II)
- Number of follicles > 10 mm on the last day of stimulation
- Total follicular mass defined by the sum of all follicular volumes (defined by the formula  $4/3 \times \pi r^3$ , where  $r=\text{radius}=\text{diameter}/2$ ) in each of the ultrasound controls.

### 3.4. Descriptive variables:

- Age
- Body Mass Index
- Stimulation days
- Total dose of gonadotrophins
- Days with antagonist GnRH

## 4. Statistical analysis

---

### 4.1. Descriptive data analysis:

Description of continuous quantitative variables (all study variables are) in their central parameters (mean and median) and dispersion values (standard deviation, p10, p25, p75, p90, maximum and minimum).

### 4.2. Intergroup homogeneity analysis:

Comparison of study groups from the point of view of basal and demographic characteristics using Student Test "t" after checking the assumption of normality using Levéne Variance Equality Test. In the case of non-parametric distribution, the Mann-Whitney test will be used.

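### Section 4.2 names Levene's variance test as the check of normality for baseline comparisons, a property that test does not measure

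*Combined protocol and SAP*

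**What the plan says.** Section 4.2 (Intergroup homogeneity analysis) covers baseline and demographic characteristics. The default is Student's t-test, applied "after checking the assumption of normality using Levéne Variance Equality Test". The fallback reads "In the case of non-parametric distribution, the Mann-Whitney test will be used". No other check of distribution is named in that section.

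Section 4.3 (Analysis of the working hypothesis) handles the same question differently. Each hormone on each stimulation day is compared by t-test "once the normal distribution of the values by means of the tests of Kolmogorov-Smirnov and Shapiro-Wilks has been verified", and by Mann-Whitney otherwise.

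Section 4.2 does not list its variables. Of the descriptive variables in section 3.4, age and "Body Mass Index" are true baseline measures. Stimulation days, total gonadotrophin dose and antagonist days arise after randomisation.

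**The concern.** The sentence in section 4.2 contradicts itself: it calls the procedure a test of equal variances and assigns it to check normality. Two arms with the same strongly skewed distribution have equal variances, so they will usually pass Levene. The rule is therefore wrong as written, and not merely short of detail.

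Two things are at stake, both modest. A report that follows section 4.2 would state that normality had been verified when it had not been examined. The section also cannot be carried out reproducibly: one analyst would apply Levene literally, and another would quietly substitute a normality test.

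**Working it through.** **The two rules side by side.** Section 4.2: Levene, then t-test or Mann-Whitney. Section 4.3: "by means of the tests of Kolmogorov-Smirnov and Shapiro-Wilks", then t-test or Mann-Whitney. The assumption to be checked is the same, but only the procedures in 4.3 test it.

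**The plan's own figure.** Section 2 bases the sample size on progesterone on the last stimulation day: 0.73 (SD 0.42) with HMG and 0.99 (SD 0.48) with FSH.
- Pooled SD = √[(0.42² + 0.48²)/2] = √0.2034 = 0.451; difference = 0.26.
- n per group = 2 × (1.96 + 0.842)² × 0.2034 / 0.26² ≈ 47.2, rounded up to 48. The t-based solution is 48.2.
- This agrees with the stated 48, and 48 × 1.15 = 55.2 gives the 55 randomised. Section 4.2 does not enter this calculation, so no sample-size figure changes. It does show that about 50 per arm is the right size for an illustration.

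**How the gate behaves on skewed data.** The documents give no baseline distributions, so the shape is assumed: two identical log-normal arms. The CV of 58% is 0.42/0.73, borrowed from last-day progesterone with HMG, which is not a baseline variable. All tests are at 5%, with 4,000 simulated data sets unless stated.

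| Assumed data | Per arm | Passes Levene (mean-centred) | Both arms pass Shapiro-Wilk |
|---|---|---|---|
| Log-normal, CV 58% | 50 | about 89% | under 1% |
| Log-normal, CV 58% | 55 | 89% | 0.15% |
| Log-normal, CV 30% | 55 | 92% | 17% |

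With the median-centred version of Levene, 95–96% pass at CV 58% and 50 per arm. More strongly skewed shapes (log-normal with log-SD 0.8, or exponential; 55 per arm, 20,000 data sets) still pass the mean-centred version in about 85–86% and the median-centred version in 95%, while Shapiro-Wilk rejects in essentially all. The tendency is strong but not absolute: roughly 5–15% of equally skewed variables would still reach Mann-Whitney.

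**What that does to the baseline p-values.** With no true difference, CV 58% and 50 per arm, the literal rule (t-test if mean-centred Levene passes, otherwise Mann-Whitney) rejects in about 3% of data sets: 3.0% in one set of 4,000 and 3.7% in a repeat. The simulation standard error is √(0.03 × 0.97/4,000) ≈ 0.3 percentage points. Used alone, the t-test and Mann-Whitney each reject in about 4–5%. The gate is conservative because the skewed data sets that fail Levene are disproportionately those in which the t-test would have been significant, and these are handed to Mann-Whitney. The two tests reach the same decision in 95–98% of data sets.

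**Comparator.** A real normality check has its own error: requiring both arms to pass Shapiro-Wilk at 5% wrongly rejects normal data in 1 − 0.95² = 9.75% of cases, which agrees with the simulated 9–10%.

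**The case against.** The strongest reply is that this is a drafting slip that merges a normality check with a variance check, and that little follows from it. The fallback is triggered by a non-normal distribution, not by a significant Levene result, so the misrouting depends on treating Levene as the sole gate. That is fair, and the conclusion is conditional on that reading. A slip still leaves the written instruction wrong, and section 4.2 offers no other check to follow.

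The illustration is also harsher than the real baseline variables. Eligibility confines age to 18–35 and BMI to below 25. The SD of age cannot exceed half its range (17/2 = 8.5 years) and its mean cannot fall below 18, so its CV is at most 8.5/18 = 47%, short of 58%. This stands: the percentages show how the gate responds and do not predict what it will do to age or BMI. The CV 30% row shows the same direction with milder skew.

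Three stronger readings are tempting, and the documents support none of them.
- *Day-1 hormones are affected.* Section 4.3 covers hormones on every stimulation day, and the schedule lists day 1 as a sampling day, so those values already have a proper normality rule.
- *Normal variables with unequal spread would be sent to Mann-Whitney.* With an assumed SD ratio of 1.8 and 50 per arm, Levene does reject in 96% of data sets. But 1:1 randomisation draws both arms from one population, so the true baseline SD ratio is 1 and Levene rejects normal data in only about 5%.
- *The baseline p-values would be seriously misleading.* The simulated rule is mildly conservative on skewed data and does not inflate error.

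**Conclusion.** The point holds as a definite error in a stated rule with a limited effect. Section 4.2 assigns a variance test to check normality and so verifies nothing about shape. If Levene is the operative gate, most skewed baseline variables would go to the t-test with normality reported as checked, and the resulting test would be mildly conservative. The size of this rests on an assumed log-normal shape and a CV that is not a baseline figure.

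The reach is baseline comparability in a randomised trial, for variables such as age and BMI. Progesterone AUC, the hormone comparisons in section 4.3 and the sample size do not depend on it. It should be corrected, but it does not threaten the trial's conclusions.

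**What to change.** In section 4.2, remove Levene's test as a check of normality and replace it with one of these:
1. Describe baseline variables by arm (mean and SD, or median and quartiles) without significance tests. This is the simpler choice, because under randomisation any chance imbalance is not a hypothesis to be tested.
2. If baseline tests are kept, judge normality within each arm by Shapiro-Wilk, as section 4.3 already does, and use Levene only to choose between the pooled and the Welch t-test.

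Either is one sentence, needs no new data, and should be settled before the data are analysed.

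A separate improvement to section 4.3, not needed to correct this error, is to adjust each hormone outcome comparison for its day-1 value. That value is already collected, so the cost is again a sentence. The plan should confirm that the day-1 sample is drawn before the first gonadotrophin dose, since the adjustment presumes a pre-treatment value.
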